**Table 2: Schedule of Events (Follow-Up Period, Unscheduled Visits, and Early Termination)**

Study Procedure	Follow-Up Period 			Unscheduled Visit 	Early Termination Visit
			EOS		
In-clinic Visit (V)	V20	V21	V22		
Week (W)	W20	W24	W28		
Study Day (D)	D141	D169	D197		
Window in days	±4	±4	±4		
Treatment:					
Study drug accountability 				X	X
TCS application	X	X	X		
TCS dispensing	X	X		X	
TCS accountability	X	X	X	X	X
Patient recording of TCS use via diary	X	X	X	X	X
Patient recording of emollient use via diary	X	X	X	X	X
Concomitant medications/procedures	X	X	X	X	X
Efficacy:					
Patient assessment of pruritus intensity using worst itch score via diary (daily)	X	X	X	X	X
Patient global impression of disease	X	X	X	X	X
Patient global impression of change	X	X	X	X	X
Patient-reported CDLQI  , POEM  , DFI  , PROMIS anxiety and depression scale 	X	X	X	X	X
IGA, EASI, GISS, SCORAD, BSA	X	X	X	X	X
Assess missed school days	X	X	X	X	X
Assess caregiver missed work days	X	X	X	X	X
Photograph AD areas (select sites)			X		X
Safety					
Weight			X		X
Height			X		X
Vital signs	X	X	X	X	X
Physical examination			X	X	X
ECG			X	X	X
Adverse events 	X	X	X	X	X
Laboratory Testing:					
Hematology			X	X	X
Chemistry			X	X	X
Urinalysis			X	X	X
Pregnancy test, WOCBP only			Urine	Urine	Urine
Biomarker:					
TARC			X	X	X
Immunoglobulin profiling			X	X	X
Drug Concentration and ADA Samples:					
Functional dupilumab concentration sample		X	X	X	X
ADA sample			X	X	X

EOS = End of Study

### 8.1.1. Footnotes for Schedule of Events Table

#### 8.1.1.1. Footnotes for Schedule of Events Table 1

1. The site will contact the patient or parents/caregiver by telephone to conduct these visits. The parents/caregiver may administer study drug during phone visits. Patients who receive study drug outside the study center will complete a dosing diary to document compliance with study drug administration and to document any related issues.  
.
3. Training of patients and parents/caregiver regarding completion of diary to record (a) administration of each dose of drug outside the clinic by parent/caregiver; (b) completion of the assessment of pruritus using worst itch scale; (c) emollient use; (d) TCS use
4. Parents/caregivers will be trained on how to administer study drug. This will enable administration at home in between clinic visits.
5. Patients will be monitored at the study site at visits 3, 5, and 7 (for patients receiving Q2W treatment) and at visits 3, 7, and 11 (for patients receiving Q4W treatment) for a minimum of 2 hours after study drug administration. Vital signs (sitting blood pressure, heart rate, respiratory rate, and body temperature) and AEs will be assessed at 30 minutes ( $\pm 10$  minutes) post-injection and then at 2 hours ( $\pm 15$  minutes).
6. Starting at visit 7, study drug will be dispensed to the parents (or caregivers) for the dose that will be administered before the next clinic visit. Parents (or caregivers) will return the study kit box (for prefilled syringes) at each subsequent in-clinic visit. At these in-clinic visits, sites will perform accountability assessment for the study drug that the parents (or caregivers) have returned to the site.
7. As per standardized regimen outlined in Section 7.2
8. The type, amount, and potency of topical products used during the study will be recorded. The amount of TCS used will be determined by weighing the tube at each visit through the end of the study.
9. Assessments/procedures should be conducted in the following order: patient reported outcomes (other than patient assessment of injection pain), investigator assessments, safety and laboratory assessments (including sample collection for ADA, PK, biomarker, ), administration of study drug, and assessment of injection pain.
10. The questionnaires will be administered only to the subset of patients or parents/caregivers who speak fluently the language in which the questionnaire is presented (based on availability of validated translations in participating countries).
11. Refer to Section 8.2.2 for details on who (parent or caregiver) is required to complete the specific questionnaires.
12. DFI is to be completed by parent/caregiver.

13. Injection pain assessment at week 2 will only be performed for patients on Q2W treatment
14. Samples will be collected before the injection of study drug
15. TB testing will be performed on a country-by-country basis, according to local guidelines if required by regulatory authorities or ethics boards.
16. Urine pregnancy testing at week 2 will only be performed for patients who receive Q2W treatment.
17. EOT is end of study for patients who enter the OLE.
18. Patients who experience adverse events of special interest related to eye disorders (refer to Section 9.4.3) will also be referred to an ophthalmologist (preferably with expertise in treating pediatric patients or Cornea and External Eye Disease [‘front-of-the-eye’] subspecialty expert). Further evaluation of these AESIs will be performed including any additional tests, if applicable, as per the discretion of the ophthalmologist.

#### 8.1.1.2. Footnotes for Schedule of Events Table 2

1. Starting at visit 4, study drug will be dispensed to the parents (or caregivers) for the dose that will be administered before the next clinic visit. Parents (or caregivers) will return the study kit box (for prefilled syringes) at each subsequent in-clinic visit. At these in-clinic visits, sites will perform accountability assessment for the study drug that the parents (or caregivers) have returned to the site.
2. Assessments/procedures should be conducted in the following order: patient reported outcomes (other than patient assessment of injection pain), investigator assessments, safety and laboratory assessments (including sample collection for ADA, PK, biomarker, ██████████), administration of study drug, and assessment of injection pain.
3. The questionnaires will be administered only to the subset of patients or parents/caregivers who speak fluently the language in which the questionnaire is presented (based on availability of validated translations in participating countries).
4. Refer to Section 8.2.2 for details on who (parent or caregiver) is required to complete the specific questionnaires.
5. DFI is to be completed by parent/caregiver.
6. Samples will be collected before the injection of study drug
7. Only for patients who do not enter the OLE.
8. Specific assessments to be performed at the unscheduled visit will depend upon the reason for the unscheduled visit.
9. Patients who experience adverse events of special interest related to eye disorders (refer to Section 9.4.3) will also be referred to an ophthalmologist (preferably with expertise in treating pediatric patients or Cornea and External Eye Disease [‘front-of-the-eye’] subspecialty expert). Further evaluation of these AESIs will be performed including any additional tests, if applicable, as per the discretion of the ophthalmologist.

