  - Acceptable documentation includes contemporaneous chart notes that record topical medication prescription and treatment outcome, or investigator documentation based on communication with the patient's treating physician. If documentation is inadequate, potential patients may be offered a course of treatment with a daily regimen of TCS of medium potency, applied for at least 28 days during the screening period (including the 2 weeks TCS standardization period). Patients who demonstrate inadequate response during this period, as defined above, will be eligible for inclusion in the study, as long as they meet other eligibility criteria.
9. At least 11 (of a total of 14) applications of a stable dose of topical emollient (moisturizer) twice daily during the 7 consecutive days immediately before the baseline visit
  10. Willing and able to comply with all clinic visits and study-related procedures
  11. Patient, either alone or with help of parents/legal guardians, as appropriate, must be able to understand and complete study-related questionnaires
  12. Parent or legal guardian must provide signed informed consent. Patients must also provide separate informed assent to enroll in the study, and sign and date either a separate informed assent form (IAF) or the informed consent form (ICF) signed by the parent/legal guardian (as appropriate based on local regulations and requirements)

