Patient and/or parents/caregiver diary completion to record self-admin of study drug (patients receiving Q2W treatment)									X				X				X		
Study drug dispensing (patients receiving Q2W treatment) 							X				X				X				
Study drug accountability (patients receiving Q2W treatment)											X				X				X

	SCN	TCS standardization	Treatment Period																
			BL						PV 8 	PV 9 	PV 10 	V 11	PV 12 	PV 13 	PV 14 	V 15	PV 16 	PV 17 	PV 18 
In-clinic Visit (V) or Phone Visit (PV)	V1	V2	V3	V4	V5	V6	V7	PV 8 	PV 9 	PV 10 	V 11	PV 12 	PV 13 	PV 14 	V 15	PV 16 	PV 17 	PV 18 	V 19
Week (W)				W1	W 2	W3	W4	W5	W6	W7	W8	W9	W10	W11	W 12	W 13	W 14	W 15	W 16
Study Day (D)	D -77 to D -14	D -14 to D-1	D1	D8	D 15	D 22	D 29	D 36	D 43	D 50	D 57	D 64	D 71	D 78	D 85	D 92	D 99	D 106	D 113
Window in days				±3	±3	±3	±3	±3	±3	±3	±3	±3	±3	±3	±3	±3	±3	±3	±3
Review home diary		X	X	X	X	X	X				X				X				X
TCS application 		X	X	X	X	X	X	X	X	X	X	X	X	X	X	X	X	X	X
TCS dispensing		X	X	X	X	X	X				X				X				X
TCS accountability 			X	X	X	X	X				X				X				X
Patient and parents/caregiver counseling for diary completion		X	X	X	X	X	X				X				X				X
Patient recording of TCS use via diary		X	X	X	X	X	X	X	X	X	X	X	X	X	X	X	X	X	X
Patient recording of emollient use via diary	X	X	X	X	X	X	X	X	X	X	X	X	X	X	X	X	X	X	X
Prior and Concomitant medications/procedures	X	X	X	X	X	X	X	X	X	X	X	X	X	X	X	X	X	X	X
Efficacy: 																			
Patient assessment of pruritus intensity using worst itch score via diary (daily)	X	X	X	X	X	X	X	X	X	X	X	X	X	X	X	X	X	X	X
Patient global impression of disease 	X		X	X			X				X				X				X

	SCN	TCS standard ization	Treatment Period																
			BL						PV 8 	PV 9 	PV 10 	V 11	PV 12 	PV 13 	PV 14 	V 15	PV 16 	PV 17 	PV 18 
In-clinic Visit (V) or Phone Visit (PV)	V1	V2	V3	V4	V5	V6	V7	PV 8 	PV 9 	PV 10 	V 11	PV 12 	PV 13 	PV 14 	V 15	PV 16 	PV 17 	PV 18 	V 19
Week (W)				W1	W 2	W3	W4	W5	W6	W7	W8	W9	W10	W11	W 12	W 13	W 14	W 15	W 16

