Study Day (D)	D -77 to D -14	D -14 to D-1	D1	D8	D 15	D 22	D 29	D 36	D 43	D 50	D 57	D 64	D 71	D 78	D 85	D 92	D 99	D 106	D 113
Window in days				±3	±3	±3	±3	±3	±3	±3	±3	±3	±3	±3	±3	±3	±3	±3	±3
Patient global impression of change 					X		X				X				X				X
CDLQI  POEM  DFI  , PROMIS anxiety and depression scale 	X		X		X		X				X				X				X
IGA, EASI, GISS, SCORAD, BSA	X	X	X	X	X	X	X				X				X				X
Faces pain scale for injection pain			X		X 3 		X				X				X				
Assess missed school days			X				X				X				X				X
Assess caregiver missed workdays			X				X				X				X				X
Photograph AD areas (select sites)			X																X
Safety:																			
Weight	X		X																X
Height	X		X																X
Vital signs 	X	X	X	X	X	X	X				X				X				X
Physical examination	X																		X

	SCN	TCS standard ization	Treatment Period																
			BL															EOT 	
In-clinic Visit (V) or Phone Visit (PV)	V1	V2	V3	V4	V5	V6	V7	PV 8 	PV 9 	PV 10 	V 11	PV 12 	PV 13 	PV 14 	V 15	PV 16 	PV 17 	PV 18 	V 19
Week (W)				W1	W 2	W3	W4	W5	W6	W7	W8	W9	W10	W11	W 12	W 13	W 14	W 15	W 16
Study Day (D)	D -77 to D -14	D -14 to D-1	D1	D8	D 15	D 22	D 29	D 36	D 43	D 50	D 57	D 64	D 71	D 78	D 85	D 92	D 99	D 106	D 113
Window in days				±3	±3	±3	±3	±3	±3	±3	±3	±3	±3	±3	±3	±3	±3	±3	±3
ECG	X																		X
Adverse events 	X	X	X	X	X	X	X	X	X	X	X	X	X	X	X	X	X	X	X
Laboratory Testing: 																			
Hematology	X		X				X				X								X
Chemistry	X		X				X				X								X
Urinalysis	X		X				X												X
Pregnancy test, WOCBP only	Ser		Ur		Ur 16		Ur				Ur				Ur				
HIV, HBsAg, HBsAb, HBcAb, Hep C Ab, TB 	X																		
Biomarker:																			
TARC	X		X				X												X
Immunoglobulin profiling	X		X																X
██████████																			
██████████																			
██████████			X																
██████████																			

	SCN	TCS standardization	Treatment Period																
			BL																EOT 
In-clinic Visit (V) or Phone Visit (PV)	V1	V2	V3	V4	V5	V6	V7	PV 8 	PV 9 	PV 10 	V 11	PV 12 	PV 13 	PV 14 	V 15	PV 16 	PV 17 	PV 18 	V 19

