3.1. The Efficacy Analysis Sets

The full analysis set (FAS) includes all randomized patients. Efficacy analyses will be based on the treatment allocated at randomization (as randomized). All efficacy variables will be evaluated in the FAS, which will be considered to be the primary analysis set.

The modified full analysis set (mFAS) includes all randomized patients but excludes potentially unblinded patients. The primary endpoint, co-primary endpoint, and selected secondary endpoints will be evaluated in the mFAS as sensitivity analyses.

The per protocol set (PPS) includes all patients in the FAS except for those who are excluded because of major protocol violations. A preliminary list of potential major protocol violations is provided in [Appendix 10.3](#) and a final list will be generated prior to database lock. The PPS will also exclude potentially unblinded patients.

The primary and co-primary endpoints will also be evaluated in the PPS.

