5.7.1. Analysis of Primary Efficacy Variable

The Cochran-Mantel-Haenszel (CMH) test adjusted by randomization strata (baseline weight group (<30 kg or ≥30kg) and region (North America or Europe) will be used for the analysis of percentage of patients with IGA 0 or 1 at week 16 or percentage of patients with EASI-75 at week 16. The Mantel-Fleiss (MF) criterion will be performed, and if it is not met while using the option CMH (MF) in SAS procedure PROC PREQ, sensitivity analyses including each factor separately in CMH test will be conducted.

All efficacy data, regardless of whether the patient remains on study treatment or discontinues the study treatment but remains in the study, will be used for analysis. Specifically, if a patient stays in the study until the end of the study planned placebo-controlled treatment period, all efficacy data collected up to the study planned end of treatment visit will be included in the primary analysis, regardless of whether the patient is on treatment or not.

Handling of dropouts or adjudicated rescue treatment or missing value for the binary response variables as the primary analysis

- If a patient withdraws from the study, this patient will be counted as a non-responder for the time points after withdrawal.
- To account for the impact of rescue treatment on the efficacy effect: if rescue treatment is used (see Section 4.3 for rescue treatment), the patient will be specified as a non-responder from the time the rescue treatment is used.
- If the patient has the missing value at week 16, then it will be counted as a non-responder at week 16.

Sensitivity analyses

1. Post-baseline Last Observation Carried Forward (LOCF) approach after censoring for rescue treatment use or study withdrawal to determine patient's status at week 16 will be conducted to assess the robustness of the primary efficacy analysis with regards to handling of missing data.
2. All observed data, regardless if rescue treatment is used or data is collected after withdrawal from study treatment will be included for analysis. Patients with missing value will be counted as non-responder.

The primary efficacy analyses will be performed on the FAS, which will be considered as the primary analysis. Evaluation of primary and co-primary endpoints in the mFAS and PPS will be considered as sensitivity analyses.

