5.7.4. Analyses of Other Efficacy Variables

The analyses of other efficacy variables will be the same as the primary analysis described in Section 5.7.1 and Section 5.7.2.

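### Children never given a language-restricted questionnaire are counted as non-responders on the binary endpoints built on it, which dilutes those response rates and differences

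*Protocol*

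**What the plan says.** In protocol Section 8.1, Table 1 attaches footnote 10 to these rows: "Patient global impression of disease 10,11", "Patient global impression of change 10,11" and "CDLQI 10,11 POEM 10,11 DFI 12 , PROMIS anxiety and depression scale 10,11". The footnote states: "The questionnaires will be administered only to the subset of patients or parents/caregivers who speak fluently the language in which the questionnaire is presented". It ties this to whether validated translations exist in the participating countries. SAP Appendix 10.2 repeats it. The DFI carries only footnote 12, and the worst-itch diary, IGA, EASI and SCORAD rows do not carry footnote 10.

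On the analysis side:

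- SAP 3.1 defines the full analysis set (FAS) as all randomized patients and says "All efficacy variables will be evaluated in the FAS". It defines no subset of patients eligible for a questionnaire.
- SAP 5.7.1, under a heading limited to binary response variables, says "If the patient has the missing value at week 16, then it will be counted as a non-responder at week 16".
- SAP 5.7.2 sends continuous endpoints to multiple imputation (MI) with ANCOVA.
- SAP 5.7.4 says "The analyses of other efficacy variables will be the same as the primary analysis described in Section 5.7.1 and Section 5.7.2".
- Inclusion criterion 11 (protocol 6.2.1) requires: "Patient, either alone or with help of parents/legal guardians, as appropriate, must be able to understand and complete study-related questionnaires".

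**The concern.** Counting a missing value as failure is a defensible convention when the value is missing because a child dropped out, was rescued or missed the visit. A child whose family speaks a language without a validated form differs in kind. That value is missing because of a fact settled before randomization, and it carries no information about how the child did. Scoring it as failure lowers the reported response rate in every arm and shrinks the reported treatment difference. These are the figures a reader would use to judge how many children felt much better or stopped itching.

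The planned analyses would not reveal the effect. The observed-data sensitivity analysis in SAP 5.7.1 also scores missing as non-response. Last observation carried forward has nothing to carry for a child who never completed the form. Appendix 10.1 lists no supportive analysis for PGI of Disease, PGI of Change or POEM.

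**Working it through.** **Which endpoints are reached.** Crossing the footnote 10 instruments with the endpoint lists in SAP 4.4.2, 4.4.3, 5.7.2 and Appendix 10.1:

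| Instrument | Binary endpoint | Continuous endpoint | In testing hierarchy |
|---|---|---|---|
| PGI of Disease | best category; best two categories | none | no |
| PGI of Change | *much better* | none | no |
| POEM | reduction ≥3; reduction ≥4 (Appendix 10.1 only) | change | change only (steps 17 and 20) |
| CDLQI | none | change | change (steps 18 and 21) |
| PROMIS | none | change | no |

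Appendix 10.1 shows a CMH method line for PROMIS but no categorical endpoint beside it. The non-responder rule therefore bites on the five binary endpoints in the first three rows, all outside the hierarchy.

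**Check of the power formula.** The documents give no power for a questionnaire endpoint. The formula used below was therefore first tried on the plan's own figures (protocol 10.2; 80 per group, two-sided 5%). With mean rate p̄, power = Φ{[|p₁ − p₂| − 1.96·√(2p̄(1 − p̄)/n)] / √[(p₁(1 − p₁) + p₂(1 − p₂))/n]}. It gives:

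- IGA 0/1, 28% vs 5%: 98.0% (plan 97%)
- IGA 0/1, 22% vs 5%: 89.0% (plan 87%)
- EASI-75, both comparisons: above 99.9% (plan 99%)

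These agree within 2 points, reading the plan's 99% as at least 99%. They do not depend on the questionnaire rule.

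**Dilution.** Let p be the response rate among children who can be given the form, and f the share who cannot. The reported rate is p(1 − f). With f equal in both arms, the reported difference is (1 − f)(p₁ − p₂), the rate ratio is unchanged, and p₁ = p₂ gives a difference of zero.

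Both f and the response rates below are assumptions, because the documents give neither. With assumed rates of 60% vs 20% (40 points):

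- f = 5%: 57% vs 19%, 38 points
- f = 10%: 54% vs 18%, 36 points
- f = 20%: 48% vs 16%, 32 points

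With 110 per arm (protocol 10.2), comparing the SAP rule with an analysis of eligible children only:

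| Assumed rates | f | Difference, SAP rule | Power, SAP rule | Difference, eligible only | Power, eligible only (n per arm) |
|---|---|---|---|---|---|
| 40% vs 15% | 0 | 25.0 | 98.9% | 25.0 | 98.9% (110) |
| 40% vs 15% | 5% | 23.75 | 98.3% | 25.0 | 98.5% (104) |
| 40% vs 15% | 10% | 22.5 | 97.6% | 25.0 | 98.0% (99) |
| 40% vs 15% | 20% | 20.0 | 95.3% | 25.0 | 96.6% (88) |
| 30% vs 15% | 0 | 15.0 | 76.3% | 15.0 | 76.3% (110) |
| 30% vs 15% | 20% | 12.0 | 64.1% | 15.0 | 66.6% (88) |

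Most of the power lost comes from having no data on these children, whichever rule is used. What the rule itself distorts is the estimate.

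**Unequal shares by arm.** Fluency and translation availability precede randomization, so f has the same expectation in each arm. With overall f = 10% and 110 per arm, the standard error of the between-arm difference in f is √(2 × 0.10 × 0.90/110) = 0.0405, about 4 points. A gap of 5% against 15% would be about 10/4.05 = 2.5 standard errors.

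**The case against.** The strongest reply is that f may be close to zero. Criterion 11 makes ability to complete the questionnaires, with help if needed, an entry requirement, and failing it is listed as a potential major protocol violation (protocol Appendix 3, SAP Appendix 10.3). That stands as a limit on size: the documents give no count, and few children may be affected. It does not close the gap. Criterion 11 concerns what the patient can do with help, while footnote 10 also turns on whether a translation exists and on the caregiver's fluency. If criterion 11 excluded every such child, the footnote would have no purpose.

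A second reply is that the reach is small and the direction conservative. That also stands: the affected endpoints are exploratory, and the expected effect works against dupilumab.

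A third is that the footnote's scope is uneven. In protocol Table 2 the equivalent footnote marks CDLQI, POEM and PROMIS but neither global impression row. That is true, but Table 1 governs Week 16.

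A reader might go further and infer that the rule manufactures treatment differences when f differs between arms. The documents do not support that. Non-administration is fixed before randomization, so any imbalance is chance variation of the kind the test already allows for; it is neither bias nor inflation of type I error.

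**Conclusion.** The point holds for five binary endpoints: two on PGI of Disease, one on PGI of Change and two on POEM. For these, the SAP as written scores children never given the form as failures, and the difference is understated by the relative amount f. That is 5% to 20% for an assumed f of 5% to 20%. The calculation assumes equal expected f across arms and compares with the response rate among children who can be given the form. The true f is unknown and may be small.

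A reader might infer that every missing Week 16 questionnaire value becomes a failure. It does not: the rule in SAP 5.7.1 covers binary variables only, CDLQI and PROMIS have no binary endpoint, and their change scores, like POEM change, go to MI. Nor is any primary, co-primary, key secondary or hierarchy endpoint affected by this rule.

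A separate gap does reach the hierarchy. A child never given POEM or CDLQI has neither a baseline nor a post-baseline value, yet SAP 5.7.2 uses baseline in both the imputation and the ANCOVA model and does not say whether such a child is imputed or dropped. The text leaves this unspecified; no harm from it has been shown.

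**What to change.** - In SAP 5.7.4, and for the POEM responder rows of Appendix 10.1, define the denominator as FAS patients eligible for the instrument: a fluent respondent and an available validated translation.
- Record eligibility as a flag for each instrument, because the respondent differs (child for the global impressions, caregiver for POEM). Base it on facts known before randomization. It must not rest on a completed baseline form, since PGI of Change has none, nor on whether a Week 16 form exists, since that would turn dropouts into ineligible children.
- Keep missing as non-response for eligible children without a Week 16 value.
- Report the number not administered for language or translation reasons by arm, and keep the all-FAS non-responder result as a sensitivity analysis.
- In SAP 5.7.2, state how children with no baseline and no post-baseline value are handled in the MI and ANCOVA for POEM, CDLQI and PROMIS change. The denominator change above should not by itself alter the population of the hierarchy endpoints.

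The cost is SAP wording and one flag per instrument. The questionnaire fields described in protocol 8.2.2 record who completed the form or whether it was read aloud, not fluency or translation availability, so the flag would need its own source. These exploratory endpoints would have a slightly smaller n. Because eligibility is fixed before randomization, the restricted comparison remains a randomized one.
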